Full study protocol and statistical analysis plan

Official Title of the study:

Implementation of a Community-based Resilience Promotion Program to

Only-child Loss Parents in China

Date of the document:

28th October 2017

Contents:

1. Participant Flow

2. Baseline Characteristics

3. Outcome Measures

4. Adverse Event Information

5. Limitations and Caveats

6. Certain Agreements

7. Results Point of Contact

1. Participant Flow

Recruitment Details

We will choose a community in Changsha, where principle investigators' institution located, to recruit the participants. This community has a number of around 260 only-child loss(OCL) parents, and has a social organization to serve the bereaved parents. The recruitment will start at Nov 1st 2017 and last around one week. The recruitment announcement will be distributed to the participants via social worker in their daily online chat group or through telephone call.

Pre-assignment Details [*]

We firstly will assess the recruited people to ensure meeting the inclusion and exclusion criteria. The inclusion criteria are made according to the official documents. OCL Family is one that has given birth to only one child but now has no living birth or adopted child, and the bereaved mother is older than 49 years (medically maximum age for fertility in China).

Those with serious mental disorders or physical illnesses who were not able to complete the intervention and evaluation questionnaire will be excluded.

Than the final enrolled participants can be sure and randomized assignment will be conducted.

Enrollment (total, anticipatory)	150			Record the number of the eligible and the excluded
Allocation (randomized)	Group A	Group B	Group C	Record the number of the received and the unreceived
	50	50	50	
Follow-up (immediately after intervention)				The numbers of each follow-up stages are uncertain by now. But in the latter research, we will record information of the lost and the continued.
Follow-up (3-month after intervention)				
Follow-up (12-month after intervention)				

Arm/Group Information *

There are three groups in the study.

Arm/Group Title *

Positive psychology therapy group= Group A

Resilience promotion therapy group= Group B

Controlled routine activity group= Group C

Arm/Group Description *§

Positive psychology therapy group will be intervened by a psychotherapy developed from an American psychologist. The positive psychology therapy lasts 8 weeks, and has a group intervention in each week. The themes of each week are start-up, time gift, positive mind, three good things, a thankful heart, life train, active service, end-up.

Resilience promotion therapy group will be intervened by another psychotherapy developed by the researchers. The resilience promotion therapy lasts 8 weeks, and also has a group intervention in each week. The themes of each week are start-up, mutual help, trust in yourself, thanksgiving feedback, care for yourself, emotional management, end-up.

Controlled routine activity group will have routine service delivered by social workers. This group will have routine service delivered by social workers.

Period(s) *

There is only one stage in the study.

Period Title *

Overall Study.

Started *

There will be 150 participants initiating the intervention.

Those 150 participants will be randomly assigned to three groups with around 50 participants in each group.

Completed *

We will do follow-up, and the number in each follow-up will be recorded.

Milestone Title [*]

Before the intervention, we will measure the participants, , and the stage is defined as T0.

We will do follow-up immediately after intervention, 3-month after intervention, 12-month after intervention, defined as T1, T2, T3 respectively.

Reason Not Completed Type [*]

We will record the exact reason (Adverse Event) why participants do not complete the study. The reason may be death, lack of efficacy, lost to follow-up, illness, withdrawal by subject or others.

2. Baseline Characteristics

Arm/Group Information *

Chi-square test will be applied to figure out the difference of enumeration data among three groups. ANOVA will be applied to test the difference of measurement data among three groups. F values and χ^2 values will be displayed to show the baseline data are no different in three groups.

Arm/Group Title *

Positive psychology therapy group

Resilience promotion therapy group

Controlled routine activity group

Arm/Group Description *§

All the recruited participants will be numbered and randomly allocated into three groups by random number table. The grouping results will be announced to the participants according to the random number table.

Overall Number of Baseline Participants *

There will be 150 participants initiating the intervention.

Baseline Measure Information *

A group of demographic characteristics will be measured in the study, including gender, age, marital status, income per month, gender of lost kid, length of lost kid.

Baseline Measure Title *

- Age * : Continuous(years)
- Gender * : Female, Male
- Marital status: with a spouse, without a spouse
- Income per month: Categorical:
 - <=1000 RMB
 - >1000 and <2000 RMB
 - >=2000 RMB
- Gender of lost kid: Female, Male
- Length of lost kid: Continuous(years)

Measure Type *

- Count of Participants: Gender, Marital status
- Mean: Age, Length of lost kid
- Number: Gender of lost kid, Income per month

Measure of Dispersion *

- Standard Deviation
- Inter-Quartile Range
- Full Range

Baseline Measure Data *

The value(s) for each baseline measure, for each group and overall cannot obtain right now since the study has not been started.

3. Outcome Measures

Outcome Measure Information *

A questionnaire will be used during each measurement, including several scales in it. The saliva test of Dehydroepiandrosterone will also be done in each measurement.

Outcome Measure Type *

- Primary

Outcome Measure Title *

- Psychological resilience: a kind of ability to bounce back from adversity measured by Connor-Davidson Resilience Scale (CD-RISC). It is a self-reported scale by adding up 25 items and the total score ranges from 0-100, with higher score reflects higher resilience. The differences within two times frame are the changes of psychological resilience
- Depression: depressive mood in recent two weeks measured by Zung Self-rated Depression Scale (SDS). It is a self-reported scale by adding up 20 items and the total score ranges from 20-80, with higher score reflects higher depression. The differences within time frames are changes of depression
- Subjective well-being: a feeling of happiness measured by Campbell Index of well-being (IWB). It is a self-reported scale by adding up 8 items and the total score ranges from 2.1-14.7, with higher score reflects higher subjective well-being. The differences within time frames are change of subjective well-being
- Social avoidance: the phenomenon that a person is absent from normal social interaction with others measured by Social Avoidance and Distress Scale(SAD). It is a self-reported scale by adding up 14 items and the total score ranges from 0-14, with higher score reflects social avoidance. The differences within time frames are the changes of social avoidance
- Sleeping quality: a reflection of one's mood in recent month measured by Pittsburgh sleep quality index(PSQI). It is a self-reported scale, with total score higher than 19 reflects sleeping disorder. The differences within each time frames are the changes of sleeping quality
- Post traumatic growth: the positive growth after an adversity measured by Post Traumatic Growth Inventory(PTGI). It is a self-reported scale by adding up 24 items and the total score ranges from 0-120, with higher score reflects more growth. The differences within time frames are changes of post-traumatic growth
- Health care behavior: a person's self-care behavior measured by Health Promoting Lifestyle Profile-II(HPLP-II). It is a self-reported scale by adding up 40 items in four dimensions. The total score ranges from 40-160, with higher score reflects better health care behavior. The differences within time frames are changes of health care behavior
- Concentration of dehydroepiandrosterone in saliva: a kind of hormone that reflects the person's psychological stress collected by Sarstedt saliva collection tube by chewing the sterile cotton strips for 60 seconds. It will be tested by enzyme-linked immunosorbent assay (ELISA) with Kit Number of HT81012 and Origin site in Canada PLLabs

Outcome Measure unit *

The psychological resilience, depression, subjective well-being, social avoidance, sleeping quality, post traumatic growth, and health care behavior are measured by scales with no unit.

Dehydroepiandrosterone has its concentration unit of pg/ml.

Outcome Measure Time Frame *

There will be four measurements, before the intervention, immediately after intervention, 3-month after intervention, and 12-month after intervention. They are defined as T0, T1, T2, T3 respectively.

Analysis Population Information

Overall Number of Participants Analyzed *

There will be 150 participants totally enrolled in the study.

Outcome Measure Data Table

Measure Type *

- Mean

Measure of Dispersion/Precision *

- Standard Deviation

Outcome Data *

The measurement value(s) for each outcome measure cannot obtain right now since the study has not been started.

Statistical Analysis Overview

Comparison Group Selection [*]

We will compare three groups' data.

Type of Statistical Test [*]

- Superiority
- Other (descriptive analysis)

P-Value [*]

P-Value will be set at 0.05.

Method [*]

- ANOVA
- Chi-Squared
- t-Test, 2-Sided
- Other: repeated measurement of variance analysis within different measurements among different groups

Estimation Parameter [*]

- Mean Difference (Final Values)

4. Adverse Event Information

Time Frame *§

The intervention lasts 8 weeks, and we will record the adverse event each week. Then we will do follow-up immediately after intervention, 3-month after intervention, and 12-month after intervention. we will record the adverse event at each follow-up.

Adverse Event Reporting Description [*]

We will add relevant information about adverse event after finishing the study.

Collection Approach for Table Default *§

- Systematic Assessment: The psychotherapist will routinely determine whether or not certain adverse events have occurred through regular investigator assessment during intervention and in each follow-up.
- Non-Systematic Assessment: Self-reporting by participants or occasional assessment by the psychotherapist.

Adverse Event Term *

The most possible adverse event may be the psychological discomfort because the participants are experiencing bereavement.

We will provide information for in three tables summarizing adverse events in each group, including all-cause mortality, serious adverse events, and other (not including serious) adverse events.

Organ System *

- Psychiatric Disorders

5. Limitations and Caveats

There may be several limitations.

We may not reach the target number of participants because the bereaved parents present social avoidance and may not interested in the intervention. We will invite social worker to help recruiting and make calls to all registered bereaved parents.

The measurements are mostly based on self-reported scales and may lead to unreliable data. We will give instruction before fulfilling the questionnaire to ensure the participants understood.

6. Certain Agreements

Are all PIs Employees of Sponsor? *

- No: The principal investigator is not an employee of the sponsor

There is no agreement between the agent(university) and the principal investigators. The principal investigators are graduate students in the university. The principal investigators (PIs) can discuss the results of the study at a scientific meeting or any other public or private forum, or to publish in a scientific or academic journal information concerning the results of the study.

7. Results Point of Contact

Name or Official Title *

Professor: [name]

Position title: Director of Nursing Psychology Research Center

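### Eligibility is set by family but parents are randomised one by one, so any couple that enrols has about a 67% chance of being split across arms, with a risk of contamination at home

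*Combined protocol and SAP*

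**What the plan says.** The eligibility rule in section 1 (Pre-assignment Details) is written for the family: "OCL Family is one that has given birth to only one child but now has no living birth or adopted child". The age condition attaches to the mother, so a father qualifies through his family and not through his own age. The pool is counted in parents: "This community has a number of around 260 only-child loss(OCL) parents". They are reached "via social worker in their daily online chat group or through telephone call", and section 5 adds that social workers will telephone every registered parent.

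Both sexes are expected ("Gender * : Female, Male"), and the baseline table includes "Marital status: with a spouse, without a spouse". It has no item on whether the spouse is also in the trial.

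Allocation is by person. Section 2 states: "All the recruited participants will be numbered and randomly allocated into three groups by random number table". Section 1 gives the sizes: "Those 150 participants will be randomly assigned to three groups with around 50 participants in each group". Participants are told their group.

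The therapies are delivered in weekly group sessions; for Group A, "The positive psychology therapy lasts 8 weeks, and has a group intervention in each week", and Group B is described likewise. The listed analyses are ANOVA, chi-squared, two-sided t-test and repeated-measures ANOVA. No family or household term appears, and the limitations in section 5 cover only recruitment shortfall and self-report.

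**The concern.** If a family meets the criterion, both parents meet it, and both will be invited. Following the allocation rule as written would then place many spouses in different arms. The session themes (gratitude, positive events, mutual help, managing emotions) are easy to pass on in conversation, and the two parents share the same bereavement.

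A control parent whose spouse attends Group A or B may receive part of that therapy second-hand. If such sharing helps, the A-C and B-C differences shrink. Couples split between A and B blur the comparison of the two therapies. Later analysis could not reliably undo this, and without a family identifier the split couples could not even be counted. This differs from correlation among people in the same therapy session: it arises from the unit of eligibility and the unit of allocation.

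**Working it through.** The plan gives no power calculation, number of couples, spouse correlation or carry-over, so there is no stated figure to reproduce.

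**Inputs from the documents:** pool of about 260 parents; 150 enrolled; arms of 50/50/50; individual allocation.

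**Assumptions:** c = 20, 60 or 130 couples in the pool; random uptake; a control with a treated spouse gains a fraction f = 25% or 50% of the therapy effect; treated participants gain nothing further from their spouse; spouse correlation 0.3.

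**Step 1. Chance that an enrolled couple is split**
- Any split: 1 - 49/149 = 100/149 = 67.1%. Simple randomisation gives 66.7%; arms of 40/50/60 give 66.2%.
- One in therapy, one in control: 2 x 50 x 100 / (150 x 149) = 44.7%.
- One in A, one in B: 2 x 50 x 50 / (150 x 149) = 22.4%.

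**Step 2. From couples in the pool to dilution**
- Couples with both parents enrolled: c x (150 x 149)/(260 x 259) = 0.332c.
- Controls with a treated spouse: couples enrolled x 0.447.
- Dilution of the therapy-control difference: (those controls / 50) x f.
- Share of participants in couples: s = 2 x couples enrolled / 150.
- Design effect of allocating by family: 1 + 0.3s.

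| Couples in pool (assumed) | Both enrolled | Split | Controls with treated spouse | Dilution, f = 25% | Dilution, f = 50% | Design effect |
|---|---|---|---|---|---|---|
| 20 | 6.6 | 4.5 | 3.0 | 1.5% | 3.0% | 1.03 |
| 60 | 19.9 | 13.4 | 8.9 | 4.5% | 8.9% | 1.08 |
| 130 | 43.1 | 29.0 | 19.3 | 9.7% | 19.3% | 1.17 |

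**Step 3. Dilution and design effect on one scale**

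Dilution costs the equivalent of a sample-size inflation of 1/(1 - dilution)^2:
- c = 20: 1.03 to 1.06, against a design effect of 1.03.
- c = 60: 1.10 to 1.21, against 1.08.
- c = 130: 1.23 to 1.54, against 1.17.
- At f = 10% the dilution cost is 1.01, 1.04 and 1.08, below the design effect in each case.

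Setting 1/(1 - s x 0.671 x f)^2 = 1 + 0.3s gives break-even at f = 22%, 21% and 20% for the three values of c.

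**Step 4. Illustration in power**

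With 50 per arm, 80% power corresponds to a standardised difference of sqrt(2/50) x (1.96 + 0.84) = 0.56. With about 20 enrolled couples, power falls to 76% (f = 25%) or 72% (f = 50%). With about 43 it falls to 72% or 62%.

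The effect on A-B is not converted to a percentage, because that needs a further assumption about what one therapy adds to someone already receiving the other.

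**The case against.** The strongest reply is that the documents establish exposure to a risk, not contamination. They are silent on whether both spouses will enrol. They give no expected share of parents with a spouse, do not say that spouses live together, and give no measure of carry-over. A current spouse may not be the child's other parent, and one spouse may volunteer alone. All of this stands, and it is why the range starts close to zero.

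Three stronger readings are tempting, and the documents support none of them.
- A reader might infer that the control group will be contaminated. That requires a number of couples and an amount of sharing that the plan does not give.
- A reader might apply the two-thirds to all participants. It applies only to couples in which both parents enrol.
- A reader might infer that at least 20 couples must enrol, since 130 families supply only 130 first parents and 150 - 130 = 20. That requires every one of the 260 parents to be paired, which sits badly with a plan that records parents without a spouse. For the same reason the 19% dilution is an extreme.

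The remedy also has a real price. At low carry-over, allocating by family loses more power than it saves. It may put spouses in the same group session, which could affect what they disclose. It leaves the community chat group open as another route between arms. These points qualify the fix. They do not remove the gap, because no safeguard appears anywhere in the plan.

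**Conclusion.** The concern holds as a design gap of uncertain size. Three things are firm: eligibility admits both parents of a family, allocation is individual, and an enrolled couple is split with probability of about 67% (45% therapy against control, 22% A against B). If sharing at home helps the untreated spouse, the bias on therapy-control differences is towards zero.

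The amount is conditional. It runs from about 1.5% to 19% dilution under the assumed 20 to 130 couples in the pool, random uptake and 25% to 50% carry-over, and falls to near zero with few enrolled couples or little sharing. Spouses volunteering together would raise the figures; spouses volunteering singly, or a recruitment shortfall, would lower them. The change is worth making before randomisation, mainly to protect against bias; a gain in power is not assured.

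**What to change.** **Change to make**
1. Record a family identifier at screening, and whether the other parent is also enrolling.
2. When both parents of a family enrol, give them one number in the random number table so that both go to the same arm. Parents enrolling alone keep their own number. Balancing the sequence by number of enrolled parents per family keeps the arms near 50.
3. Add a family random effect, or family-clustered standard errors, to the outcome models.

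**Cost.** One sentence in the allocation procedure, one data field and one model term, with no extra participants or staff. Final enrolment is confirmed before randomisation, so couples can be identified in time. The plan should state the downsides: the design effect of about 1.03 to 1.17 (at the assumed correlation of 0.3) and its break-even with dilution, slightly unequal arms, spouses possibly in the same sessions, and the remaining chat-group route.

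**If individual allocation is kept.** Still record the family identifier, include the family term, report the number of split couples by type, and run a sensitivity analysis that excludes them.

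**One parent per family** also prevents splitting but shrinks the pool. With 60 couples there are 260 - 60 = 200 families, so 150 participants need 150/200 = 75% uptake, against 150/260 = 58% now. Section 5 already doubts that the target will be reached.

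### Arms A and B are treated in groups, but no planned outcome test has a therapy-group term, so T1–T3 standard errors are too small if outcomes correlate within groups

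*Combined protocol and SAP*

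**What the plan says.** **Allocation is individual.** Section 2, Arm/Group Description: "All the recruited participants will be numbered and randomly allocated into three groups by random number table". Section 1, Started: "Those 150 participants will be randomly assigned to three groups with around 50 participants in each group".

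**Treatment in A and B is delivered in groups.** Section 1, Arm/Group Description, on A: "The positive psychology therapy lasts 8 weeks, and has a group intervention in each week". On B: "The resilience promotion therapy lasts 8 weeks, and also has a group intervention in each week". On C it says only "Controlled routine activity group will have routine service delivered by social workers", which leaves open whether that service is given in groups.

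**Outcome methods.** The Method list in section 3 names ANOVA, chi-squared, a two-sided t-test and, under Other, "repeated measurement of variance analysis within different measurements among different groups". In that phrase, groups are the three arms, as section 1 defines Groups A, B and C. The significance level is 0.05 and the test type is superiority.

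**Timing.** T0 precedes treatment: "Before the intervention, we will measure the participants" (section 1, Milestone Title). T1, T2 and T3 all follow it. Baseline comparability is tested separately in section 2 ("Chi-square test will be applied to figure out the difference of enumeration data among three groups", with ANOVA for continuous measures).

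The documents do not state how many therapy groups each arm has, how large they are, how participants are placed in them, or whether membership is recorded. They mention no random effect, cluster-robust variance, ICC or design effect.

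**The concern.** This is an individually randomised trial with group treatment. People who meet weekly for 8 weeks share a facilitator, a discussion and each other's company, and one of B's themes is mutual help. Their later scores may therefore be more alike than those of two people from different groups in the same arm.

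The listed tests treat participants within an arm as independent. Repeated-measures ANOVA allows for correlation within a person over time, but not for correlation between members of one therapy group. Individual randomisation does not remove the problem, because this correlation arises after allocation.

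If the correlation is positive, the standard error of any comparison involving A or B is understated. A chance difference between particular therapy groups can then be reported as a therapy effect. All eight outcomes are typed as primary, so every main comparison is exposed.

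**Working it through.** **The plan's own figure.** The plan gives no power calculation, effect size, SD or ICC. Only the allocation can be checked: 3 × 50 = 150, which agrees.

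**Inputs from the documents.** 50 per arm; two-sided level 0.05; group sessions in A and B.

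**Assumed inputs.** Therapy-group size m = 10, 25 or 50 (50 is one group per arm, which the text permits); ICC = 0.01, 0.05 or 0.10; C ungrouped; one post-baseline time point.

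**Formulas.**
- Design effect in A and B: DE = 1 + (m − 1) × ICC. In C it is 1.
- True SE divided by independence SE: √((DE + 1)/2) for A or B v C; √DE for A v B.
- True type I error = 2 × [1 − Φ(1.96 / ratio)].

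**Worked case, m = 10, ICC 0.05.** DE = 1 + 9 × 0.05 = 1.45.
- v C: ratio √(2.45/2) = 1.107; 1.96/1.107 = 1.77; type I error 7.7%.
- A v B: ratio √1.45 = 1.204; 1.96/1.204 = 1.63; type I error 10.4%.

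**All cases (formula).**

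| m | ICC | DE | A or B v C | A v B |
|---|---|---|---|---|
| 10 | 0.01 | 1.09 | 5.5% | 6.0% |
| 10 | 0.05 | 1.45 | 7.7% | 10.4% |
| 10 | 0.10 | 1.90 | 10.4% | 15.5% |
| 25 | 0.01 | 1.24 | 6.4% | 7.8% |
| 25 | 0.05 | 2.20 | 12.1% | 18.6% |
| 25 | 0.10 | 3.40 | 18.6% | 28.8% |
| 50 | 0.01 | 1.49 | 7.9% | 10.8% |
| 50 | 0.05 | 3.45 | 18.9% | 29.1% |
| 50 | 0.10 | 5.90 | 29.1% | 42.0% |

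**Simulation check** (40,000 null replicates per setting, pooled t-test and three-arm ANOVA).
- ICC 0: all tests at 4.9–5.1%.
- m = 10, ICC 0.05: 7.6% (v C), 10.3% (A v B), 10.1% (three-arm ANOVA).
- m = 50, ICC 0.10: 29.8%, 43.6% and 49.2%.

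**If C's service is also grouped at the same size,** its comparisons take the ratio √DE as well, so the v C column becomes the A v B column.

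**Repeated-measures ANOVA, T0–T3** (10,000 replicates; within-person correlation 0.5 assumed; no group effect at T0; ICC 0.05). Type I error of the arm-by-time test:
- Group effect lasting to T3: 9.3% (m = 10), 18.1% (m = 25).
- Group effect fading to zero by T3: 9.3% and 17.2%.
- No clustering: 5.0%.

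Simulated t-tests at T0 stay at 4.6–5.4%.

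**The case against.** **The size rests on assumptions.** This stands. No group size or ICC is given, and with groups of 10 and ICC 0.01 the tests are close to nominal. A reader might infer that this trial's p-values will be badly wrong. The documents do not support that; they support only that the correlation is ignored and that the consequence may be anything from trivial to severe.

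**The role of the t-test is not stated.** This also stands. The Method list does not say whether it compares arms or time points within an arm. Listing the mean difference in final values as the estimation parameter suggests a between-arm use but does not settle it. The pairwise figures describe a between-arm comparison and should not be read as the error rate of a test the plan has specified. The three-arm and repeated-measures ANOVAs are affected either way. Chi-squared, if used to compare arms on a post-baseline outcome, also assumes independence.

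**Group effects may fade.** In part. If the group effect is gone by T3, t-tests at T3 are at about 5%, and the repeated-measures arm main effect falls from 10.1% to 6.1% (m = 10) or from 18.0% to 8.4% (m = 25). The arm-by-time test remains inflated.

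**Three further inferences go too far.**
- The baseline tests are not faulty on this account, because T0 precedes any session.
- A v B is the worst-affected comparison only if C's service is ungrouped.
- The text does not establish that each arm meets as a single group of 50, although it allows it.

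**Conclusion.** The concern holds as a conditional statement. The omission is certain: treatment in A and B is given in groups, and no listed outcome method allows for it. The harm depends on a positive within-group correlation at T1–T3 and on a group structure that the plan does not give.

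Under the assumed range (groups of 10 to 50, ICC 0.01 to 0.10, C ungrouped, one time point), true type I error at nominal 5% is about 5.5–29% for A or B v C and 6–42% for A v B. At size 10 and ICC 0.05 it is about 8% and 10%, and about 10% for the three-arm ANOVA. At the top of the range, with one group per arm, a different model would not help, because therapy and group are then fully confounded.

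This should be fixed before the trial starts. Membership that is not recorded may be impossible to recover later.

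**What to change.** 1. Record each participant's therapy group. State the number of groups per arm, and whether C's routine service is given in groups.
2. Replace the T1–T3 tests with a mixed model that has a participant effect and a random therapy-group intercept in A and B (in C only if its service is grouped), with Satterthwaite or Kenward–Roger degrees of freedom.
3. If an arm meets as a single group, its group variance cannot be estimated. State that the therapy effect cannot be separated from that group's effect, and limit the conclusion accordingly.
4. Leave the baseline tests as they are on this account.

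**Cost.** One recorded variable, a different model, wider intervals and lower but honest power. As illustration, assume a standardised difference of 0.5, ICC 0.05, one time point, no baseline adjustment and C ungrouped. Nominal power, ignoring groups, is 0.70. With k groups per arm, allowing for groups (noncentral t; 2(k − 1) df for A v B, Satterthwaite df v C):
- Five groups of 10: A v B has noncentrality 0.5/√(2 × 1.45/50) = 2.08 on 8 df, power 0.45. v C has 0.5/√(2.45/50) = 2.26 on 21.2 df, power 0.58.
- Two groups of 25: A v B has 0.5/√(2 × 2.20/50) = 1.69 on 2 df, power 0.17. v C has 0.5/√(3.20/50) = 1.98 on 4.2 df, power 0.34.

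With only two groups per arm the variance estimate is fragile. In simulation the adjusted v C test had type I error 6.5% (and power 0.38, partly for that reason), against 5.1% with five groups.

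How many groups to run is for the sponsor to decide. More groups mean more sessions, so that is a delivery decision and not a free analytic correction.

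### Baseline F and chi-square tests cannot show that the three arms are alike; drop that claim and pre-specify adjustment for the T0 outcome and length of loss

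*Combined protocol and SAP*

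**What the plan says.** - **Baseline tests.** Section 2 (Arm/Group Information) plans chi-square tests for counts; for continuous variables, "ANOVA will be applied to test the difference of measurement data among three groups". The stated purpose is that "F values and χ^2 values will be displayed to show the baseline data are no different in three groups".
- **Variables.** Section 2 (Baseline Measure Title) lists six: age, gender, marital status, income, the child's gender, and "Length of lost kid: Continuous(years"). I read the last as time since the child's death; the document does not define it.
- **Eligibility.** Section 1 (Pre-assignment Details) defines the family by the loss and by the mother's age: "OCL Family is one that has given birth to only one child but now has no living birth or adopted child". It sets no limit on time since the loss.
- **Allocation.** "All the recruited participants will be numbered and randomly allocated into three groups by random number table", with "Those 150 participants will be randomly assigned to three groups with around 50 participants in each group". No stratification is stated.
- **Outcome analysis.** Section 3 (Statistical Analysis Overview) lists ANOVA, chi-square, t-test and "repeated measurement of variance analysis within different measurements among different groups". The estimation parameter is a difference in mean final values. No covariate is named. "P-Value will be set at 0.05".

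**The concern.** The plan fixes the conclusion of the baseline tests in advance and treats failure to reject as evidence of equality. Under proper randomisation the null hypothesis of these tests is true by design, so neither a large nor a small p-value says whether an observed imbalance matters. That depends on the size of the imbalance and on how strongly the variable predicts outcome.

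Length of loss is the clearest example. It is unrestricted at entry and could plausibly relate to depression, avoidance or growth. It is collected, but it has no stated part in the outcome analysis. If one arm happened to hold more recently bereaved parents, part of the observed difference between arms would reflect that, while the report stated that the arms did not differ. The opposite error is also open: a chance significant baseline test has no planned interpretation.

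**Working it through.** The plan gives no figure of its own to reproduce here.

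**Inputs from the document:** three arms of about 50 (taken as 50); one-way ANOVA; six baseline variables; level 0.05, which is stated for the outcome analysis and assumed here for the baseline tests.

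**Assumptions:** correlation r between length of loss and an outcome of 0.2 to 0.4 (other values shown where used); SD of length of loss of 3, 5 or 8 years. The document gives neither. Dropout and clustering are ignored.

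**1. Largest gap that passes.** The critical value of F(2, 147) at 0.05 is 3.058. Put the arm means at +d/2, 0 and −d/2 in SD units. Then F = 50 × 2 × (d/2)² / 2 = 12.5 d², so d = √(3.058 / 12.5) = 0.49 SD. If instead one arm stands apart from two equal arms, F = 50 × (2d²/3) / 2 = 16.67 d², and d = √(3.058 / 16.67) = 0.43 SD. A gap of 0.49 SD is about 1.5, 2.5 or 4.0 years for an SD of 3, 5 or 8 years.

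**2. How often it arises.** The standard error of a two-arm gap is √(2/50) = 0.20 SD.
- A gap of 0.49 SD or more in a given pair corresponds to z = 0.495 / 0.20 = 2.47, a two-sided probability of about 1.3%.
- The mean absolute gap in a given pair is 0.20 × √(2/π) = 0.16 SD.
- In 40,000 simulated trials, about 24% had a largest between-arm gap above 0.3 SD with a non-significant F. About 83% of gaps above 0.3 SD went unflagged.

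**3. Effect on an unadjusted comparison.** The shift is r × d.

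| r | Gap 0.49 SD (limit) | Gap 0.16 SD (average) |
|---|---|---|
| 0.2 | 0.10 SD | 0.03 SD |
| 0.3 | 0.15 SD | 0.05 SD |
| 0.4 | 0.20 SD | 0.06 SD |

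The smallest significant difference at 50 per arm is 1.96 × 0.20 = 0.39 SD. For the shift alone to reach it, r must be 0.392 / 0.495 = 0.79 or more.

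**4. False-positive rate.** Conditional on a 0.49 SD gap, the two-sided rate for that pair is 7.3% at r = 0.2, 10.3% at r = 0.3 and 20.2% at r = 0.5. Over all randomisations the simulated rate is about 4.9%. Given a non-significant baseline F it is 4.8% at r = 0.3 and 4.4% at r = 0.5.

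**5. Precision forgone.** Adjusting for one covariate cuts residual variance by r²: 4%, 9% and 16% for r = 0.2, 0.3 and 0.4.

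**6. Chance significance.** For six independent tests, 1 − 0.95⁶ = 26%.

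**The case against.** The strongest reply is that simple randomisation is valid without adjustment. The unadjusted standard error of 0.20 SD already contains chance imbalance in length of loss, and step 4 confirms that the overall error rate holds. The extreme gap is rare. Section 2 also plans summary measures by arm, so a reader will see the size of any imbalance. The scale outcomes are described as changes between time frames, and a group-by-time analysis that includes T0 removes stable differences due to length of loss. All of this stands. It limits the point to conditional bias and precision. It does not rescue the quoted purpose of the tests. The group-by-time analysis leaves any effect of length of loss on trajectory, and the final-value mean difference lacks even that protection.

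Three stronger readings are tempting, and the document supports none of them:

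- **That the tests miss imbalances large enough to mimic a treatment effect.** At r = 0.2 to 0.4 the worst unflagged gap gives 0.10 to 0.20 SD, at most about one standard error and well short of 0.39 SD.
- **That open entry on time since loss is itself a flaw.** No range or SD is given, and broad entry is defensible when 150 participants must come from about 260 parents.
- **That a chance significant result would be taken as failed randomisation.** The plan states no action. Counting the eight T0 outcomes as further tests would raise the 26% to 1 − 0.95¹⁴ = 51%, but the plan does not say that they will be tested, and correlated scales would bring the figure down.

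**Conclusion.** The point holds in a limited form. The baseline tests cannot do what the plan asks of them, in either direction: near half an SD can pass unflagged, and about one correctly randomised trial in four would show at least one chance significant difference among six independent tests. The consequence for the treatment comparison is modest: a conditional shift of at most about 0.10 to 0.20 SD under the assumed correlations, usually nearer 0.03 to 0.06 SD, plus some avoidable loss of precision. It falls mainly on the final-value estimate.

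The gap and the 26% rest on 50 per arm, a 0.05 level and, for the 26%, independence. The shift rests on an assumed correlation and on reading the variable as time since the death. It would be wrong to infer that the trial's inference is invalid or that the error rate is inflated overall.

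**What to change.** 1. In section 2, delete the statement that F and chi-square values will show no difference. Report means, SDs, counts and standardised differences by arm, without p-values.
2. In section 3, pre-specify the adjustment. For example:

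> Group comparisons at T1, T2 and T3 will adjust for the participant's T0 value of the same outcome and for years since the child's death. Both covariates are fixed in advance and will be used whatever the baseline table shows. The estimate reported will be the adjusted mean difference.

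3. Define the length-of-loss variable explicitly as years from the child's death to T0, if that is what is meant.
4. Optionally, split the enrolment list at the median length of loss and use the random number table within each half. This is practical because section 1 settles enrolment before allocation, but the point does not depend on it.

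Both covariates are already collected. The cost is SAP wording, one or two of the 147 residual degrees of freedom in each comparison, and slightly more analysis work.
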